##### **4.6.2 Clinical Laboratory Test Results**

All clinical laboratory data will be stored on the database in the units in which they were reported. Patient listings and summary statistics at each assessment time will be presented using the International System of Units (SI units; *Système International d'Unités*). Laboratory data not reported in SI units will be converted to SI units before processing.

Laboratory test values will be presented by individual listings with flagging of values outside the normal ranges.

##### **4.6.2.1 Standard Reference Ranges and Transformation of Data**

Roche standard reference ranges, rather than the reference ranges of the Investigator, will be used for all parameters. For most parameters, the measured laboratory test result will be assessed directly using the Roche standard reference

range. Certain laboratory parameters will be transformed to Roche's standard reference ranges.

A transformation will be performed on certain laboratory tests that lack sufficiently common procedures and have a wide range of Investigator ranges, e.g., enzyme tests that include AST, ALT, and alkaline phosphatase and total bilirubin. Given that the standard reference ranges for these parameters have a lower limit of zero, only the upper limits of the ranges will be used in transforming the data.

#### **4.6.2.2 Definition of Laboratory Abnormalities**

For all laboratory parameters included, there exists a Roche predefined standard reference range. Laboratory values falling outside this standard reference range will be labeled "H" for high or "L" for low in patient listings of laboratory data.

In addition to the standard reference range, a marked reference range has been predefined by Roche for each laboratory parameter. The marked reference range is broader than the standard reference range. Values falling outside the marked reference range that also represent a defined change from baseline will be considered marked laboratory abnormalities (i.e., potentially clinically relevant). If a baseline value is not available for a patient, the midpoint of the standard reference range will be used as the patient's baseline value for the purposes of determining marked laboratory abnormalities. Marked laboratory abnormalities will be labeled in the patient listings as "HH" for very high or "LL" for very low.

#### **4.6.3 Vital Signs**

Vital signs data will be presented by individual listings with flagging of values outside the normal ranges and flagging of marked abnormalities. In addition, tabular summaries will be used, as appropriate.

#### **4.6.4 ECG Data Analysis**

ECG data will be presented by individual listings with flagging of values outside the normal ranges and flagging of marked abnormalities. In addition, tabular summaries will be used, as appropriate.

#### **4.6.5 Anti-Drug Antibody Data Analysis**

The number and percentage of patients who test positive for plasma antibodies to RO6867461 at baseline and at the study visits will be tabulated, but not for treatment arm A.

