1.2.1 Previous Nonclinical Studies

Pharmacological studies were performed in vitro and in vivo to investigate the target binding affinity, specificity, and biological activity of RO6867461. In vitro studies demonstrated that RO6867461 binds the target molecules VEGF and Ang-2 with high affinity. Mutations in the Fc region of RO6867461 abolish binding to Fc γ receptors, located on effector cells, and the neonatal Fc receptor (FcRn).

Pharmacological evaluation in vivo demonstrated that RO6867461 reduces the formation of CNV, the leakiness of existing CNV lesions, and subsequent injury to the retina due to lesion formation in a mutant mouse model of early bilateral CNV and a laser-induced model of CNV in cynomolgus monkeys ([RO6867461 Investigator's Brochure](#))

Following single intravitreal (IVT) administration of 1.5 mg/eye RO6867461 in cynomolgus monkeys, flip-flop pharmacokinetics were observed with a strong correlation between exposure in vitreous humor, aqueous humor, and systemic circulation; with systemic bioavailability of 13%.

In a 2-month Good Laboratory Practice (GLP) study in cynomolgus monkeys, the ocular and extra-ocular findings following three IVT injections of the highest 3 and 6 mg/eye/dose were consistent with an immune-mediated response to a humanized antibody, like RO6867461, in nonhuman primates. The no-observed-adverse-effect level (NOAEL) was established at a dose of 1.5 mg/eye/dose for IVT administration.

In a 6-month GLP study in cynomolgus monkeys, no changes were observed following seven IVT injections every 4 weeks at the low dose of 0.5 mg/eye/dose comprising the NOAEL. Dose-dependent ocular inflammatory cell infiltration and clinical signs of ocular inflammation occurred in RO6867461-treated eyes at 1.5 or 1.5/3 mg/eye/dose IVT following the same dosing schedule. Ocular findings generally correlated with the systemic presence of anti-drug antibodies (ADAs) against RO6867461 and exposure loss in the serum of all animals. Immunohistochemistry detection of immune-complex deposits in the affected eyes of RO6867461-treated animals is currently ongoing.

RO6867461 did not induce any neurological (CNS) findings or effects on heart rate/electrocardiogram (ECG) endpoints (including QT and QTc [corrected QT interval]), respiratory rate, or body temperature in cynomolgus monkeys up to 6 months treatment.

See the [RO6867461 Investigator's Brochure](#) for details on nonclinical studies.

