6.5.5 Anti-Drug Antibody Data Analysis

The number and percentage of patients who test positive for plasma antibodies to RO6867461 at baseline and at the study visits will be tabulated.

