Appendix 1 Schedule of Assessments (cont.)

Week	Screening	Week 1		Week 4	Week 8	Week 12	Week 13	Week 16	Week 20	Week 24	Week 28	Week 32	Week 36 Final Visit	Early Termination Visit	Unscheduled
		Day 1	Day 7	Day 28	Day 56	Day 84	Day 91	Day 112	Day 140	Day 168	Day 196	Day 224	Day 252		
Visit Window			+/-3	+/-7 ¹	+/-7 ¹	+/-7 ¹	-4/+3 ^m	+/-7 ¹	+/-7 ¹	+/-7 ¹	+/-7 ¹	+/-7 ¹	+/-7	+7	
Assessments															
Fundus Fluorescein Angiography ^a	x					x							x	x	x
IndoCyanine Green Angiography ^a	x					x							x	x	x
PK Sample ^a		x		x		x	x	x		x			x	x	x
PD Biomarkers Sample ^a		x		x		x	x	x		x			x	x	x
Exploratory Plasma Biomarker Sample ^a		x		x		x				x			x		x
Aqueous Humor Sample (optional) ^{a,c,e,f}		x						x	x			x			x
Vitreous Humor + Blood Samples (optional) ^{c,e,g}															x
Clinical Genotyping Sample ^{a,h,i}		x													
Anti-Drug Antibody (ADA) ^a		x		x		x		x		x			x	x	x

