#### **2.2.6 Safety Outcome Measures**

The safety outcome measures for this study are as follows:

- Incidence and severity of ocular adverse events
- Incidence and severity of non-ocular adverse events
- Incidence of laboratory abnormalities, based on hematology, clinical chemistry, and urinalysis test results
- Incidence of anti-RO6867461 antibodies
- ECGs
- Vital signs
- Other safety biomarkers

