#### **4.6 SAFETY ANALYSES**

All safety analyses will be based on the safety analysis population. The LoPO contains the full list of reports for safety analyses.

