##### **Secondary:**

The secondary objectives of this study are as follows:

- To assess the safety of multiple intravitreal (IVT) doses of RO6867461
- To assess systemic pharmacokinetics of RO6867461
- To investigate pharmacodynamics (PD) and anatomical outcomes informing on the mechanism of action of RO6867461
- To investigate the formation of plasma anti-RO6867461 antibodies
- To investigate 2 different RO6867461 dosing regimens

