#### **STATISTICAL METHODS**

##### **SAFETY ANALYSES**

All patients who receive at least one administration of the study treatment will be included in the safety analysis. The safety data, including adverse events, reasons for withdrawal from study, laboratory data, concomitant medications, vital signs, and physical examination results will be listed and summarized descriptively.

As appropriate, listings, summary tables, and graphs (subject plot and/or mean plots) will be provided for safety and tolerability assessments.

Anti-RO6867461 antibody results (positive/negative) will be listed.

General adverse events will be listed and summarized by body system and preferred term using MedDRA. Ophthalmologic adverse events will be listed and summarized.

For laboratory data subject listings will be presented with abnormalities flagged.

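### SAP 4.6.5 tabulates antibody positivity visit by visit, which gives a lower bound on the stated outcome, the incidence of anti-RO6867461 antibodies, but not the incidence itself

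*SAP*

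**What the plan says.** - **Outcome and objective.** SAP 2.2.6 lists "Incidence of anti-RO6867461 antibodies" as a safety outcome, as does Protocol 3.3.1. The secondary objectives (Protocol 2.2; synopsis in SAP Appendix 1) include "To investigate the formation of plasma anti-RO6867461 antibodies".
- **Tabulation.** Protocol 6.5.5: "The number and percentage of patients who test positive for plasma antibodies to RO6867461 at baseline and at the study visits will be tabulated". It names no arms. SAP 4.6.5 plans the same table and restricts it: "at baseline and at the study visits will be tabulated, but not for treatment arm A".
- **Other outputs.** The synopsis in SAP Appendix 1 adds: "Anti-RO6867461 antibody results (positive/negative) will be listed". SAP 4.6 also points to a List of Planned Outputs: "The LoPO contains the full list of reports for safety analyses". That list is not part of the documents.
- **Sampling.** The schedule (Protocol Appendix 1; SAP Appendix 2) has ADA samples on Day 1 and at Weeks 4, 12, 16, 24 and 36, plus early termination and unscheduled visits. No arm is exempted. On dosing days the sample is taken before treatment.
- **Exposure.** Arm A receives only ranibizumab. Arm E receives three ranibizumab injections up to Week 8 and then six of RO6867461, the first at Week 12.

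Neither document defines treatment-emergent ADA, a count of patients positive at any time after exposure, a denominator, the handling of patients positive before exposure, or an ADA baseline for Arm E.

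**The concern.** Incidence and formation both refer to patients who lacked the antibody and then acquired it. The percentage positive at a visit is point prevalence. A patient positive at Week 12 and negative at Week 36 is absent from the Week 36 row. Four positives at Week 12 and four at Week 24 may be four patients or eight. In Arm E, two rows after Day 1 describe patients who have not yet had the drug.

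The protocol gives a reason to want this number. In the 6-month monkey study, "Ocular findings generally correlated with the systemic presence of anti-drug antibodies (ADAs) against RO6867461 and exposure loss in the serum of all animals". If the clinical report gives only visit rows, a reader cannot say how many patients in each arm formed antibodies, nor compare the arms on that basis.

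**Working it through.** The documents state no ADA rate, so there is no figure of the plan's to reproduce. The check asks what the planned table can and cannot determine.

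**1. Which samples are post-exposure** (arm definitions and ADA schedule)

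| Arm | First RO6867461 | Samples before exposure | Samples after exposure |
|---|---|---|---|
| B, C, D | Day 1 | Day 1 | Weeks 4, 12, 16, 24, 36 (five) |
| E | Week 12 | Day 1, Week 4, pre-dose Week 12 | Weeks 16, 24, 36 (three) |
| A | never | all six | none |

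**2. Bounds from visit rows.** Take n patients, b positive before exposure, and v positive at each of m post-exposure visits, with every scheduled sample available. The denominator is n − b.

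- Lower bound: v − b, not below 0. The earlier positives persist and the same new patients are positive throughout.
- Intermediate case: m × (v − b). The earlier positives persist, but the new positives are different patients at each visit.
- Upper bound: m × v, capped at n − b. The earlier positives revert and different patients are positive at each visit.

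**3. Numbers.** Arm sizes are from SAP 2.3; b and v are assumptions.

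| n | b | v | m | Lower | Intermediate | Upper |
|---|---|---|---|---|---|---|
| 45 | 2 | 2 | 5 | 0/43 (0%) | 0/43 (0%) | 10/43 (23.3%) |
| 45 | 2 | 4 | 5 | 2/43 (4.7%) | 10/43 (23.3%) | 20/43 (46.5%) |
| 45 | 0 | 4 | 5 | 4/45 (8.9%) | 20/45 (44.4%) | 20/45 (44.4%) |
| 68 (Arm E) | 3 | 6 | 3 | 3/65 (4.6%) | 9/65 (13.8%) | 18/65 (27.7%) |

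For the second row: 4 − 2 = 2; 5 × (4 − 2) = 10; 5 × 4 = 20; 45 − 2 = 43. Visit rows fix the incidence only in trivial cases, such as no positives at any visit.

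**4. Unexposed reference left in the table without Arm A.** Day 1: 3 × 45 = 135 patients in Arms B, C and D, plus 68 in Arm E, is 203. Weeks 4 and 12: the 68 in Arm E. Weeks 16, 24 and 36: none, because only Arm A is still unexposed then.

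**5. Why a background reference helps an any-time count.** If a fraction f of samples is falsely positive, independently, the chance of at least one positive in m samples is 1 − (1 − f)^m. The documents give no f. For f = 1%, 2% and 5% this is 4.9%, 9.6% and 22.6% with m = 5, and 3.0%, 5.9% and 14.3% with m = 3. If reactivity recurs in the same patients, the figures are lower.

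**The case against.** **The data are not lost.** Results are listed as positive or negative, so conversions and transient positives can be counted from the listing, and the List of Planned Outputs may contain more. This stands: a reader might infer that incidence is unobtainable, and the documents do not support that. But a listing is not a definition. The pre-exposure reference, the denominator and the treatment of earlier positives would be chosen after the results are visible.

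**The upper bounds are extreme.** They need every positive to be transient and in a different patient. That is fair; they show what the table leaves open, not what is likely.

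**Pre-existing positives need not mislead.** A reader might infer that visit rows overstate drug-induced antibody by some factor. The baseline row is in the same table. With an assumed 5% positive at baseline, 5% induced among the rest and all positives persisting, a visit row shows 0.05 + 0.95 × 0.05 = 9.75%. Subtracting the baseline gives 4.75%, and dividing by 0.95 returns 5%. No fixed inflation follows. What the baseline row cannot correct is transience and the lack of linkage.

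**Dropping Arm A does not remove every control.** A reader might infer that no unexposed reference remains. Arm E supplies one through the pre-dose Week 12 sample, and Day 1 rows exist for Arms B, C and D. Arm A is not needed to count emergent cases. Nor does the protocol expressly require Arm A in the table, since its sentence names no arms.

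**The consequence is limited.** ADA is a descriptive safety summary with no test or decision rule. The protocol attributes the 2-month monkey findings to an immune response to a humanized antibody in nonhuman primates, so their relevance to patients is uncertain. This limits the weight of the point. It does not reconcile the outcome with its table.

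**Conclusion.** The point holds as a mismatch between the named outcome and its planned analysis. The outcome is incidence; the table is prevalence by visit. It gives a lower bound for each arm, provided that for Arm E the reader recognises which rows precede exposure. The gap between the bounds can be wide: 4.7% to 46.5% in one example for an arm of 45, and 4.6% to 27.7% in one for Arm E. Those figures rest on assumed counts and complete sampling. That visit rows alone do not determine incidence does not depend on them, apart from the trivial cases.

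Arm A's exclusion is a lesser matter: it removes the unexposed reference at Weeks 16, 24 and 36 only, and the SAP gives no reason for it. Sample size, power and the efficacy analyses are unaffected.

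**What to change.** In SAP 4.6.5:

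1. Add, for each RO6867461 arm, the number and percentage of patients with treatment-emergent ADA: negative at the last sample before the first RO6867461 injection (Day 1 for Arms B, C and D; pre-dose Week 12 for Arm E) and positive at any later sample.
2. Define the denominator as patients negative before exposure with at least one post-exposure result. Arm E patients who leave before receiving RO6867461 then drop out of it.
3. Show patients positive before exposure separately.
4. Keep the per-visit table as support, with Arm E's Week 4 and Week 12 rows marked as pre-exposure.
5. Show Arm A as the background reference for Weeks 16 to 36 if its samples are assayed, or state why it is excluded.

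A treatment-boosted category based on titre should not be added on the present text: the documents describe positive/negative results and mention no titre.

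The cost is SAP wording and one extra table, and possibly the assay of Arm A samples that the schedule already collects. No visit or sample is added.

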#### **4.6.6 Ocular Assessments**

Results of the following ocular assessments will be summarized by time point for the study eye using descriptive summaries: BCVA (also for the non-study eye), IOP (also for the non-study eye), and changes from baseline in these measurements will be tabulated.

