3.3 OUTCOME MEASURES

3.3.1 Safety Outcome Measures

The safety outcome measures for this study are as follows:

- Any relevant safety observations derived from BCVA (modified early treatment diabetic retinopathy study [ETDRS] charts), slit lamp examination, dilated binocular indirect high-magnification ophthalmoscopy, intraocular pressure (IOP), fundus photography (FP), SD-OCT, and angiography
- Incidence and severity of ocular adverse events
- Incidence and severity of non-ocular adverse events
- Incidence of laboratory abnormalities, based on hematology, clinical chemistry, and urinalysis test results
- Incidence of anti-RO6867461 antibodies
- ECGs
- Vital signs

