4.6.4.1 Ocular Safety Assessments

Ocular assessments will be performed as detailed in the SoA ([Appendix 1](#) and [Appendix 2](#)) and include:

- BCVA using the ETDRS-like charts (see Section [4.6.4.2](#)); performed prior to dilating eyes.
- Slit lamp examination (scales for grading flare/cells and vitreal hemorrhage density are detailed in [Appendix 3](#))
- Dilated binocular indirect high-magnification ophthalmoscopy
- Retinal imaging: FP, SD-OCT and angiographies
- IOP measurement: If IOP ≥ 30 mmHg at 30 (± 5) minutes post-treatment administration in the study eye, then it should be measured again at 60 (± 10) minutes post-treatment administration.
- Assessment of ocular perfusion performed as soon as possible, but not later than 15 minutes post-injection, using finger counting, hand movement, or light perception as appropriate

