5.1.4 Sight-Threatening Adverse Events (Immediately Reportable to the Sponsor)

An AE is considered to be sight threatening and serious, and should be reported by the Investigator to the Sponsor immediately (i.e., no more than 24 hours after learning of the event; or reporting instructions) if it meets one or more of the following criteria:

- It causes a decrease of ≥ 30 letters in BCVA (compared with the last assessment of VA prior to the most recent treatment) lasting more than 1 hour
- It requires surgical intervention (i.e., conventional surgery, vitreous tap, or biopsy with IVT injection of anti-infectives, or laser or retinal cryopexy with gas) to prevent permanent loss of sight
- It is associated with severe intraocular inflammation (i.e., 4+ anterior chamber cell/flare or 4+ vitritis; see the definitions of intraocular inflammation in Section 5.3.5 and grading scales for assessment in Appendix 3
- In the opinion of the Investigator, it may require medical intervention to prevent permanent loss of sight

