5.3 METHODS AND TIMING FOR CAPTURING AND ASSESSING SAFETY PARAMETERS

The Investigator is responsible for ensuring that all AEs (see Section 5.1.1 for definition) are recorded on the Adverse Event eCRF and reported to the Sponsor in accordance with instructions provided in this section and in Sections 5.4-5.6.

For each AE recorded on the Adverse Event eCRF, the Investigator will make an assessment of seriousness (see Section 5.1.2 for seriousness criteria), severity (see Section 5.3.3), and causality (see Section 5.3.4).

5.3.1 **Adverse Event Reporting Period**

Investigators will seek information on adverse events at each patient contact. All AEs, whether reported by the patient or noted by study personnel, will be recorded in the patient's medical record. AEs will then be reported on the Adverse Event eCRF as follows:

After informed consent has been obtained **but prior to initiation of study treatment**, only SAEs caused by a protocol-mandated intervention should be reported (e.g., SAEs related to invasive procedures such as angiographies). Any other AE should not be reported.

After initiation of study treatment, all AEs, regardless of relationship to study treatment, will be reported until the final visit.

After a period of 28 days from the last dose of study treatment, Investigators should report any deaths, SAEs, or other AEs of concern that are believed to be related to prior treatment with study treatment (see Section 5.6).

5.3.2 **Eliciting Adverse Event Information**

A consistent methodology of non-directive questioning should be adopted for eliciting AE information at all patient-evaluation time-points. Examples of non-directive questions include the following:

“How have you felt since your last clinic visit?”

“Have you had any new or changed health problems since you were last here?”

5.3.3 **Assessment of Severity of Adverse Events**

Table 3 provides guidance for assessing AE severity.

Table 3 Adverse Event Severity Grading Scale

Severity	Description
Mild	Discomfort noticed, but no disruption of normal daily activity
Moderate	Discomfort sufficient to reduce or affect normal daily activity
Severe	Incapacitating with inability to work or to perform normal daily activity

Note: Regardless of severity, some events may also meet seriousness criteria. Refer to definition of a serious adverse event (see Section 5.1.2).

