6.5.6 Ocular Assessments

Results of the following ocular assessments will be summarized by time-point using descriptive summaries: BCVA, IOP, slit lamp examination, indirect ophthalmoscopy, FFA, ICGA, FP, SD-OCT, and FAF.

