## **2.2 OUTCOME MEASURES**

For efficacy analyses only measurements in the study eye are used; except where explicitly stated.

For safety analyses events and measurements in both eyes will be included in the analyses, except for imaging.

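### SAP 2.2.6 and 4.6.6 omit, without a stated reason, the slit-lamp and ophthalmoscopy safety summaries the protocol commits to, so eye inflammation is reported as AE terms and not by examination grade

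*SAP*

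**What the plan says.** Protocol 3.3.1 opens its list of safety outcome measures with "Any relevant safety observations derived from BCVA (modified early treatment diabetic retinopathy study [ETDRS] charts), slit lamp examination", and goes on to ophthalmoscopy, IOP and imaging. Protocol 6.5.6 turns this into an analysis commitment: "Results of the following ocular assessments will be summarized by time-point using descriptive summaries: BCVA, IOP, slit lamp examination, indirect ophthalmoscopy", followed by five imaging methods. Protocol 4.6.4.1 says the slit-lamp examination is graded ("scales for grading flare/cells and vitreal hemorrhage density are detailed in" Appendix 3). Under Protocol 4.3.3 the physician who evaluates the ocular assessments is masked to treatment.

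The SAP is narrower. SAP 2.2.6 carries over the other six safety outcomes of Protocol 3.3.1 and adds "Other safety biomarkers", but leaves out the ocular-examination outcome. SAP 4.6.6 reads: "ocular assessments will be summarized by time point for the study eye using descriptive summaries: BCVA (also for the non-study eye), IOP", with changes from baseline in these measurements. SAP 2.2 sets the general rule: "For safety analyses events and measurements in both eyes will be included in the analyses, except for imaging". SAP 4.6 refers to the LoPO for the complete set of safety reports.

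**The concern.** A safety outcome that the protocol names, and says will be summarized over time, has no specific table in the SAP text. SAP 2.2 does not explain this, because its only exception is for imaging.

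Ocular inflammation is the finding for which this matters most. Protocol 1.2.1 describes dose-dependent inflammatory cell infiltration and clinical signs of inflammation in treated eyes in the 6-month monkey study, generally correlated with anti-drug antibodies. SAP 4.6.5 tabulates those antibodies by visit (except in Arm A). The SAP text plans no matching table of inflammation grade by visit to read beside it. The slit-lamp grades are masked, use a fixed scale and are already scheduled. Without a table, the study report could describe inflammation only through what was recorded as an AE and how that AE was scored.

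**Working it through.** There is no stated figure to reproduce. The check compares the two documents and then asks whether another planned output fills the gap.

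**Step 1. Count the assessments.**

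| Assessment | Protocol 6.5.6 | SAP 4.6.6 | Imaging |
|---|---|---|---|
| BCVA | yes | yes | no |
| IOP | yes | yes | no |
| Slit lamp | yes | no | no |
| Indirect ophthalmoscopy | yes | no | no |
| FFA, ICGA, FP, SD-OCT, FAF | yes (5) | no | yes |

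Named in the protocol: 9. Kept in the SAP: 2. Omitted: 9 − 2 = 7. Omitted and imaging: 5. Omitted and not imaging: 7 − 5 = 2. Protocol 4.6.4 lists the ocular images sent to the reading center. They are exactly the five in the last row, so slit lamp and ophthalmoscopy fall outside the imaging exception.

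**Step 2. Does the AE route capture inflammation?** Yes, as events. Protocol 5.3.5 defines iritis by inflammatory cells in the anterior chamber, with no grade threshold. It gives flare alone its own AE term and counts vitreous cells from trace upward as vitritis. SAP 4.6.1 summarizes ocular AEs with the study eye separate. It does not mention arms, but SAP 4.1.2 assigns safety patients to treatment groups. The 4+ threshold in Protocol 5.1.4 ("It is associated with severe intraocular inflammation (i.e., 4+ anterior chamber cell/flare or 4+ vitritis") governs immediate reporting as a serious event, and 4+ also stops treatment under Protocol 4.7.1.1. It does not decide whether a finding is recorded as an AE.

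**Step 3. What does the AE route not show?**
- Grade. Protocol 5.3.3, Table 3, scores severity by effect on daily life. Mild, for example, is "Discomfort noticed, but no disruption of normal daily activity". Trace cells and 3+ cells could both be mild. Because SAP 4.6.6 tabulates no grade at all, 4+ is missing along with the rest.
- Course by visit. Under Protocol 5.3.5.3 a persistent event is entered once and its severity is raised to the worst level reached. The rise and fall across visits is not visible.
- Findings not recorded as AEs. Ophthalmoscopy or slit-lamp observations that do not become an AE have no specific table.

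**Step 4. Look at the visits soon after a dose.** In Protocol Appendix 1, Day 7 and Week 13 have slit lamp, ophthalmoscopy and IOP but no BCVA. IOP is therefore the only result that SAP 4.6.6 would summarize at those two visits.

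**The case against.** The strongest defence has three parts.

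First, inflammation is not lost. Study eyes with inflammation of trace or above are excluded at entry (Protocol 4.2.2), so later findings should normally be new. The AE definitions have no grade threshold, and ocular AEs are summarized for the study eye. The Internal Monitoring Committee also reviews safety data. This stands. A reader might infer from SAP 4.6.6 that inflammation below 4+ has no planned result by arm. The documents do not support that: such inflammation falls under the AE terms in Protocol 5.3.5 and enters the SAP 4.6.1 summaries.

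Second, the protocol synopsis attached as SAP Appendix 1 still lists slit lamp and ophthalmoscopy under ocular safety, and promises tabular and graphical output for safety assessments where appropriate. So the SAP does not disown the outcome. But this wording is general. It does not commit to a table of either examination, and the specific section, SAP 4.6.6, names only two assessments.

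Third, SAP 4.6 places the complete list of safety reports in the LoPO, so SAP 4.6.6 need not be exhaustive and the tables may exist there. This cannot be ruled out. It limits the point to the SAP text. If the LoPO does list them, SAP 2.2.6 and 4.6.6 still differ from the protocol and should be corrected.

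It is also fair to say that the protocol asks for descriptive summaries and does not specify their layout.

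**Conclusion.** The point holds as a conflict between the protocol and the SAP text. Two non-imaging safety examinations of the nine assessments in Protocol 6.5.6 have no specific summary in SAP 4.6.6, the matching outcome is missing from SAP 2.2.6, and no reason is given. What is lost is the examination grade at all levels, its course by visit, and findings not recorded as AEs. The occurrence of inflammation, as AE terms by treatment group, is not lost.

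The loss cannot be expressed as a number from the documents. A reader might try to size it by counting scheduled examinations, by comparing trial doses with the monkey no-effect dose, or by putting an upper limit on a rate with no cases observed. None of these measures it. Visit counts are not an effect on a conclusion, and the dose ratio is a toxicology argument. A zero-case limit would be nearly the same from the AE count, and the documents never state that the six Phase I patients given repeated 6 mg had no inflammation.

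The conclusion assumes that the SAP sections are followed as written and that the LoPO does not already contain the tables. The primary efficacy analysis is unaffected. The correction is worth making because it is cheap and the data are already scheduled.

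**What to change.** - In SAP 2.2.6, restore the ocular-examination outcome of Protocol 3.3.1.
- In SAP 4.6.6, add descriptive study-eye tables by arm and visit, including Day 7 and Week 13. They should cover anterior chamber cell grade, flare grade, vitreous cell grade and ophthalmoscopy findings.
- If the summaries were dropped on purpose, say so in the SAP and give the reason as a change from the protocol.
- If the LoPO already lists these tables, align SAP 2.2.6 and 4.6.6 with it.

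Two additions are optional and go beyond what the protocol asks. One is each patient's worst post-baseline grade, counted once. The other is to split Arm E at the pre-dose Week 12 examination, since that arm is on ranibizumab before it and RO6867461 after it.

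The cost is some SAP wording and a few tables from examinations already scheduled. No new data, test or endpoint is needed. Counts will be small, so the tables should stay descriptive.
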